11.0 STATISTICAL CONSIDERATIONS

11.1 OVERVIEW

This protocol will assess the proportion of clinical tumor responses, defined as progression-free survival at 6 months, and the toxicities associated with high-dose ^{153}Sm -EDTMP (MTD at 30 mCi/kg) after an initial lower dose of the agent along with external beam radiation therapy in patients with high-risk osteogenic sarcoma.

Primary objective: The primary objective of this study is to determine if the addition of external beam radiation therapy to infusional ^{153}Sm -EDTMP can delay the progression of target lesions. The primary endpoint is 6-month progression free survival (PFS). It is a combined effect of the entire treatment. To be evaluable, patients must meet all eligibility criteria, including signing a consent form, and have completed treatment according to protocol without major deviations. Patients who are enrolled but unevaluable will be replaced on the study. Only patients enrolled on Stratum 1 (i.e., with a diagnosis of osteosarcoma) will be evaluated for the Primary Objective.

Secondary objectives:

1. Describe the short and long-term toxicity profile of combined treatment with ^{153}Sm -EDTMP and external beam radiation therapy.
2. Estimate the local control rate. (Stratum 1 only)
3. Determine the overall survival (OS). (Stratum 1 only)
4. Describe the distribution of absorbed doses delivered to each targeted lesion and the distribution of equivalent uniform doses delivered to each patient.
5. Model the relationship between absorbed doses and time to progression.
6. Determine the correlation of hypoxic volume and maximum tumor/blood ratio obtained by [^{18}F]-MISO PET scanning with patient outcomes.

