11.2 STUDY DESIGN

This is a single-arm study with 2 strata: Stratum 1 for patients with osteosarcoma, and Stratum 2 for patients with other high risk solid tumors. Stratum 2 is exploratory in nature, and the goal of including these patients is to facilitate accomplishing secondary objectives related to toxicity and the feasibility of administering this treatment regimen to solid tumor patients. If possible, we will, however, use patients on Stratum 2 to estimate response rates of tumors other than osteosarcoma. For Stratum 1, 6-month PFS as the primary endpoint. The study will pre-specify target lesions for each patient in Stratum 1 that will be used to assess PFS, with the intention that every lesion radiographically evident at the time of enrollment will be a target lesion. Events will be the first disease progression at any of the target lesions or death from any cause. All patients treated on Stratum 1 will be included in the determination of PFS, regardless of treatment modification or discontinuation. The design will include interim analyses for futility if it seems unlikely that the treatment has sufficient activity. The historical PFS in 11 patients treated with ¹⁵³Sm-EDTMP similar to how we are proposing, but without the external beam component, was 15.8%. For this study of ¹⁵³Sm-EDTMP plus external beam radiation therapy, a 6-month PFS of 35% would be the lowest that would be considered acceptable, and PFS that is convincingly worse than this would be considered grounds for discontinuing further study. The non-parametric Kaplan-Meier estimate will be used to monitor the PFS function. After 8 patients have been enrolled, the design will include an interim analysis for futility that could halt the trial if it seems likely that this regimen does not have sufficient clinical activity. The study is designed to stop if we are 80% certain that the 6-month PFS is below 15%.

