11.3 STATISTICAL ANALYSIS PLAN

11.3.1 Estimate the PFS for subjects treated on Stratum 1.

Sample size: The primary measure of efficacy will be PFS at 6-months for Stratum 1 patients. In specific, the 6-month PFS for this treatment will be compared to a reference of 15.8% (hazard rate = 0.308/person-month i.e. median of 2.25 months). In patients with metastatic osteosarcoma a 6-month PFS of 35% would be considered promising, and is the benchmark for this study. Assuming exponential survival, 4 patients per year will be accrued for 5 years (20 total), one year of additional follow-up, and a one-sided 0.05 alpha level test, the sample size of 20 will have 82% power to detect a hazard ratio of 1.76.

Early stopping guideline for safety: The study will be monitored after every patient for non-hematologic grade 4 toxicities following initiation of external beam radiation therapy. This stopping rule for toxicity will hold enrollment if the posterior probability of risk being larger than 0.2 is 75% or higher. The prior for this toxicity monitoring rule is beta (1, 5). This distribution means that our prior guess at this type of grade 4 toxicity is 16.7%, and there is 95% probability that it is between 0.51% and 52.2%. The operating characteristics of the stopping rule are shown below and are based on 5000 simulations:

Toxicity stopping rule:

Study termination if:	2 AEs	3 AEs	4 AEs	5 AEs	6 AEs
And number of patients between:	2 - 3	4 - 7	8 - 12	13 - 16	17 - 20

Operating characteristics of stopping rule based on 5000 simulations:

True Toxicity Risk	Prob. Declare Treatment Too Toxic	Avg. Sample Size
0.05	1.0%	19.8
0.10	6.4%	19.2
0.15	17.1%	17.9
0.20	33.7%	16.2
0.25	54.0%	13.8
0.30	69.1%	12.0
0.35	82.9%	9.7
0.40	92.6%	7.9

Early stopping guideline for futility and simulations: Simulation is used to demonstrate the operating characteristics of the study for a sample size of 20. The study will be monitored for futility with a primary endpoint of 6-month PFS. The non-parametric Kaplan-Meier estimate will be used to estimate the PFS function at 6-months. After 8 patients have been enrolled, the design will include an interim analysis for futility that could halt the trial if it seems likely that the treatment does not have sufficient clinical activity.

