Toxicities will be graded according to CTCAE v4.0 and the RTOG Cooperative Group Common Toxicity Criteria, and attributable toxicities grade 3 or higher will be recorded. For purposes of evaluation, we will consider toxicities resulting from the administration of ¹⁵³Sm-EDTMP separately from toxicities resulting after initiation of external beam radiation therapy. [However, we will hold accrual after enrollment of five patients to evaluate cumulative toxicity from the combined regimen.] Adjustments to external beam therapy in response to toxicity would be made in accordance with standard Radiation Oncology treatment protocols and clinical judgment.

11.3.3 Describe the distribution of absorbed doses delivered to each targeted lesion and the distribution of equivalent uniform doses delivered to each patient.

The total absorbed dose delivered to each targeted lesion will be limited by the tolerance of surrounding normal tissue. We will produce histograms showing the distribution of radiation absorbed doses by lesion, and summarize the results by patient for the lesion receiving the lowest absorbed dose in each patient. With a sample size of 20 patients, we will be able to estimate the proportion of patients whose lesions are all treated to an absorbed dose of ≥ 80 Gy with a precision of $\pm 23\%$.

11.3.4 Model the relationship between absorbed dose and time to progression for patients enrolled in Stratum 1.

We expect a total dose of 80 to 100 Gy to produce a local control rate of 80%, while a total absorbed dose of 60 to 70 Gy may produce a local control rate of 50 – 70%, and the local control rate would decline steeply at lower absorbed doses. We will use a generalized mixed effects model treating dose and time as fixed effects and the random effect of individual patients for the outcome of progression of each targeted lesion. If at least 10 patients have at least one lesion that receives a radiation dose with similar effectiveness to our historical control experience, and at least one lesion receiving the targeted dose, this analysis would have 80% power to demonstrate a significant dose-response with alpha 0.05.

11.3.5 Determine overall and progression-free survival for patients enrolled in Stratum 1.

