12.1 REPORTING OF ADVERSE REACTIONS

12.1.1 Definitions

12.1.11 An **adverse event** is any new, undesirable medical occurrence or change of an existing condition in a subject that occurs during treatment (which may include a specified post treatment period), whether or not considered to be product related. Abnormal laboratory findings considered by the reporting physician to be clinically significant, e.g. those that are unusual or unusually severe for the population being studied, should be recorded as adverse events.

12.1.12 A **serious adverse event** is defined by regulatory/clinical criteria. It is one that suggests a significant hazard or side effect, regardless of the investigator's or sponsor's opinion on the relationship to study material. This includes, *but may not be limited to*, any event that (at any dose):

- is fatal;
- is life threatening (places the subject at immediate risk of death);
- requires in-patient hospitalization or prolongation of existing hospitalization; or
- is persistent and results in significant disability/incapacity.

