12.1.2 Investigator's Reporting Obligations

12.1.2.1 Grade 4 (life-threatening) or grade 5 (fatal) adverse events that are unexpected (no listed on the package label) with an attribution of possible, probable, or definite must be reported to the FDA within 10 business days.

12.1.2.2 Reports to the FDA should be submitted in writing (FDA Form 3500 MEDWATCH) to:

[name]
[name] 20993
Ph. [name]
[contact]
www.fda.gov/medwatch

with a copy simultaneously submitted to the Johns Hopkins Institutional Review Board.

12.1.2.3 Johns Hopkins Institutional Review Board reporting requirements: The Organization has the responsibility to report unanticipated problems involving

risk to subjects or others under [Policy 103.6\(b\)](#), serious or continuing non-compliance under [Policy 103.7](#), and suspension or termination of approved research under [Policy 113.1](#), to the appropriate agencies. The Institutional Official (IO) is authorized as the individual who will submit reports when an IRB has made a determination under the three cited policies. In cases where the IRB and IO determine that additional information is required before submitting a final report, a preliminary report may be made to the appropriate officials, supporting federal agency (as applicable), OHRP, and FDA (as applicable), within one month of the IRB's determination.

12.1.2.4 A draft preliminary or final report will be prepared for review by the IO and General Counsels (GCs). The draft report will contain the following information:

- The nature of the event
- The findings of the organization
- The actions taken by the organization and IRB, including plans to protect the rights and welfare of the participants
- The reasons for the organization's and IRB's actions
- The plans for continued oversight or investigation or action.

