The draft report will be finalized by the IO and the GCs. The IO will sign the report within 20 days of the agreed upon final revision of the report. The final report will be submitted to the OHRP if the research is conducted, funded, or overseen by DHHS; to FDA, if the research is regulated by FDA; and to other agencies that are signatories to the Common Rule [1], if the research is conducted, funded or overseen by that agency. A copy of the report will be sent to the reviewing IRB, ORA if the project is funded by an outside sponsor, Risk Management (if applicable), and the PI. The IO may determine the report should be provided to the Director of the department in which the PI is appointed as faculty and the Dean of the School of Medicine. If the event involves unauthorized use, loss, or disclosure of PHI, a copy will be sent to the HIPAA Privacy Officer. 12.7.2.3 All toxicities should be recorded on the flow sheet.

12.1.2.5 Notify the P. I. immediately of any fatal toxicity.

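### Section 11.3.2 limits the toxicity record to attributable events of grade 3 or higher, in conflict with section 12; in a single-arm trial the profile then depends on a subjective filter

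*Combined protocol and SAP*

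**What the plan says.** **Objective.** Section 11.1 lists as its first secondary objective: "Describe the short and long-term toxicity profile of combined treatment". No limit to attributable events is stated. Section 3.2.1 has the same aim.

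**Analysis section.** Section 11.3.2 grades toxicities by CTCAE v4.0 and RTOG criteria and says that "attributable toxicities grade 3 or higher will be recorded". It does not say who attributes, by what rule, or to which component of treatment.

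**Section 12.** Section 12.1.1 defines an adverse event "whether or not considered to be product related", and defines a serious event irrespective of anyone's opinion on relationship. Section 12.1.2 adds: "All toxicities should be recorded on the flow sheet". Attribution appears in section 12 as a trigger for expedited reports: unexpected grade 4 or 5 events "with an attribution of possible, probable, or definite must be reported to the FDA within 10 business days".

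**Safety rule.** Under section 11.3.1 the study is "monitored after every patient for non-hematologic grade 4 toxicities following initiation of external beam radiation therapy", and the rule will "hold enrollment if the posterior probability of risk being larger than 0.2 is 75% or higher". Section 12.2 refers back to this rule and adds no attribution condition.

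**Design.** Section 11.2: "This is a single-arm study with 2 strata".

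**The concern.** Sections 11.3.2 and 12.1.2 both govern what is recorded, and they differ. One keeps attributable events of grade 3 or higher; the other keeps all toxicities, with no limit on attribution or grade. Section 13 provides for several participating sites, so two sites could each follow the protocol and keep different data.

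The narrower rule matters more here than it would in a randomised trial. No comparison group shows the background rate of severe events. Patients receive two samarium infusions, external beam therapy and a stem cell infusion within weeks, some after ifosfamide mobilisation, and all have unresectable or metastatic tumour. Assigning a severe event to treatment or to disease is then largely opinion, made by people who know the treatment given. If unattributed events are not kept, nobody can later check how much the filter removed. At stake is the first secondary objective; the primary analysis of 6-month progression-free survival is not touched.

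**Working it through.** **1. The texts side by side**

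| Place | What is kept or counted | Attribution condition | Grade condition |
|---|---|---|---|
| 11.3.2 | Toxicities recorded | Attributable | 3 or higher |
| 12.1.1 | Adverse event, by definition | None | None |
| 12.1.2 | Toxicities on the flow sheet | None | None |
| 12.1.2.1 | Expedited FDA report | Possible, probable or definite | 4 or 5, unexpected |
| 11.3.1 | Stopping rule count | None | 4, non-hematologic, after external beam therapy starts |

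The first and third rows conflict. The fourth governs reporting, so it does not explain the first. The fifth defines its event by type, grade and timing. Its boundary table counts AEs, a term that 12.1.1 defines without regard to relationship.

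**2. Direction of the effect on the profile**

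Let p be the all-cause risk of a qualifying event per patient, and f the share of patients with such an event whose event is judged attributable. The recorded risk is p × f. Since f ≤ 1, it cannot exceed p. The documents give no f. With p = 0.30 for illustration:

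- f = 0.9: 0.30 × 0.9 = 0.27
- f = 0.8: 0.30 × 0.8 = 0.24
- f = 0.5: 0.30 × 0.5 = 0.15

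**3. The plan's stopping rule reproduced**

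Inputs from 11.3.1: prior Beta(1, 5), risk threshold 0.2, posterior cut-off 75%, maximum 20 patients.

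- Prior mean: 1/(1 + 5) = 16.7%; 95% interval 0.51% to 52.2%. Both as stated.
- Boundary at n patients: the smallest x with P(Beta(1 + x, 5 + n − x) > 0.2) ≥ 0.75. For example, 3 events in 7 patients give Beta(4, 9) and 0.795; 4 in 12 give Beta(5, 13) and 0.758. All stated boundaries (2, 3, 4, 5, 6 events) reproduce.
- Stop probability by an exact patient-by-patient binomial recursion:

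| True risk | 0.05 | 0.10 | 0.15 | 0.20 | 0.25 | 0.30 | 0.35 | 0.40 |
|---|---|---|---|---|---|---|---|---|
| Plan (%) | 1.0 | 6.4 | 17.1 | 33.7 | 54.0 | 69.1 | 82.9 | 92.6 |
| Exact (%) | 1.1 | 6.2 | 17.4 | 34.1 | 53.0 | 70.3 | 83.4 | 91.9 |

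The largest gap is 70.3 − 69.1 = 1.2 points. The simulation standard error there is √(0.703 × 0.297/5000) = 0.65 points, so the gap is within simulation error. The rule's arithmetic is sound.

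**4. What would follow if the filter reached the rule**

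This is conditional, because the documents do not say that it does. Replace the true risk p by p × f in the same recursion:

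| Share uncounted (1 − f), assumed | Stop probability, true risk 0.20 | Stop probability, true risk 0.30 | Average N, true risk 0.30 | Stop probability, true risk 0.40 |
|---|---|---|---|---|
| 0% | 34.1% | 70.3% | 11.7 | 91.9% |
| 10% | 26.9% | 60.3% | 13.0 | 85.5% |
| 20% | 20.4% | 49.3% | 14.4 | 76.1% |
| 50% | 6.2% | 17.4% | 17.9 | 34.1% |

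**The case against.** **The sections can be read together.** The sentence in 11.3.2 does not say that attributable events alone are recorded. It may name the subset summarised for this objective, with the flow sheet holding everything. That is a fair reading, and if sites work this way no data are lost. But both places speak of recording, and 11.3.2 promises no all-cause table. The summary would still be filtered.

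**Attributable toxicity may be the right target.** The objective concerns toxicity of the treatment. These are poor-risk, heavily pre-treated patients, with a reference median progression-free survival of 2.25 months (11.3.1), so some severe events will come from disease. Removing those moves the figure towards the treatment-caused rate. This stands in part: the understatement is relative to all-cause incidence, not necessarily to the true treatment effect. Without a control arm, though, a reader cannot tell correct exclusions from wrong ones unless both rates are shown.

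**There are other safeguards.** Section 11.3.2 holds accrual after five patients to review cumulative toxicity, and section 12 provides for monitoring by the principal investigator and annual committee review. These stand, although the plan does not say which record feeds the five-patient review.

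**A stronger reading to resist.** A reader might infer that the filter also biases the stopping rule's count downward. The documents do not support that. The rule carries no attribution condition, counts AEs, and is nowhere said to draw on records kept under 11.3.2.

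**Conclusion.** The inconsistency between 11.3.2 and section 12 is real and stands in the current text. If 11.3.2 is followed as worded, the toxicity profile depends on an unspecified and subjective judgement, and can only equal or fall below all-cause incidence. The shortfall cannot be sized from the documents, because the share judged unrelated is not given; the f values of 0.5 to 0.9 above are assumptions.

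For the stopping rule, no defect is shown. Its boundaries and operating characteristics reproduce. The fall at a true risk of 30%, from about 70% to 60%, 49% or 17%, shows only why the source of the count should be stated. It rests on two things absent from the plan: a filter applied to that count, and the assumed shares of 10%, 20% and 50%.

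This is a minor point about a secondary objective, worth correcting because the correction is easy.

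**What to change.** - In 11.3.2, state that all toxicities of grade 3 or higher are recorded and tabulated regardless of attribution, with attributable events shown as a subset.
- Make attribution a separate field, and say who assigns it and on what scale.
- In 11.3.1, confirm that the stopping rule, which has no attribution condition, counts all qualifying events regardless of attribution, and name the record from which the count is taken.
- Say whether grades 1 and 2, which section 12.1.2 does not exclude from the flow sheet, are to be summarised.

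The cost is a few sentences. Section 12.1.2 already requires the flow-sheet data, so little extra collection is needed, and the attributed rate is still reported. The drawback is that the all-cause rate will include some disease-related events and look higher; printing both rates makes this visible.

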3.2.5 Stratum 1 Only

To observe overall survival and time to progression in patients treated with combined infusional ^{153}Sm -EDTMP and external beam radiation therapy, and model any relationship between total absorbed dose and progression.

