5.2 EXCLUSION CRITERIA

5.2.1 Patients must not be pregnant or breastfeeding. Sexually active patients are strongly advised to use accepted, effective forms of contraception.

5.2.2 Patients who have received prior radiotherapy to all areas of current active disease are ineligible.

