6.2 OVERALL TREATMENT PLAN

This is a treatment protocol to establish the safety and efficacy of radiation therapy consisting of high-dose ^{153}Sm -EDTMP and external beam radiotherapy for the treatment of high-risk osteogenic sarcoma and solid tumors with bony metastases. The primary endpoint will be clinical response of tumor lesions, defined as either stable disease or decrease in the size of the tumor by radiographic imaging (which may include CT or MRI) using RECIST 1.1 criteria. Progression will be defined as appearance of new lesions or expansion of current lesions by 20% as per RECIST 1.1 criteria. In some patients, additional information on clinical response may be obtained from histology (percent tumor necrosis) in cases where patients proceed to resection or biopsy following radiation therapy. Other treatment endpoints include progression-free and overall survival. We will obtain post-treatment [^{18}F]-MISO and [^{18}F] FDG PET scans to be analyzed but these images will not be used to define clinical response.

The first administered activity of ^{153}Sm -EDTMP will be a low “tracer” infusion administered at 1 mCi/kg on Day 1. Using the 3-dimensional dosimetry package 3D-RD, we will perform three-dimensional dosimetry using SPECT images after administration of the “tracer” activity to determine the distribution of dose delivered to the tumor and the surrounding normal tissues. As quickly as feasible (goal is within seven days), using the dosimetric results from the tracer administration, a combined treatment plan will be designed aimed at delivering the target dose to the entire tumor. This plan will be designed using methodology uniquely available at Hopkins (3D-RD software); we will import the 3-dimensional absorbed dose map resulting from ^{153}Sm -EDTMP therapy, adjusted to correspond to the fractionation schedule used in external beam radiotherapy, into the external beam planning system (Pinnacle), by fusing (registering) the SPECT/CT and absorbed dose map with the external beam planning CT, allowing a treatment plan to be generated from the combination of (1) scaling of the tracer absorbed dose map to the requisite ^{153}Sm therapeutic activity and (2) external beam fields designed to optimally complement the radiopharmaceutical absorbed dose map to deliver a target of 75 Gy to each and every tumor voxel while respecting normal organ constraints (25).

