The first portion of the combined plan, that is, the second, “treatment” ^{153}Sm -EDTMP infusion, will then be implemented on Day 8. Maximum activity administered will be 30 mCi/kg, which is the maximally tolerated dose permitting recovery of myelosuppression with auto-stem cell infusion (14). After the “treatment” infusion, SPECT scans will again be performed to confirm total dose delivered and subsequently adjust the external beam portion of the treatment plan, as necessary. External beam radiotherapy will begin as early as possible between Days 15 and 22. The total dose to be used will be modified based on surrounding tissue tolerances. On Day 24, previously harvested autologous peripheral blood or bone marrow stem cells will be infused in order to ameliorate the expected myelosuppression. External beam radiation therapy will not be administered on Day 24 (anticipated to be a Friday), nor on Days 25 or 26, in order to provide time for infused hematopoietic stem cells to home to the bone marrow and leave the circulation.

Patients will be reimaged one month following completion of external beam radiation by CT/MRI for evidence of clinical response (defined as stable disease or better by RECIST 1.1 criteria) or disease progression. In the event of progression of a single lesion, local therapy such as radiofrequency ablation or cryoablation may be provided so that the response of stabilized lesions can continue to be monitored. If suspicious lesions remain on

thoracic CT scan or on MRI of the primary site after the completion of therapy, further evaluation by biopsy may be clinically indicated, and potentially surgical intervention pursued if persistent disease is found. Percent necrosis of any resected tumor will be evaluated pathologically.

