6.2.5 Planning and administration of external beam radiation therapy

Initial planning CTs for radiation therapy will be performed just prior to initiation of therapy. After each samarium infusion, if tolerable, the patient will be placed in a reproducible treatment position using an appropriate immobilization device based on treatment site while data from SPECT/CT is obtained. Alternatively, the two CT

components will be co-registered and combined fields generated. Subsequent radiation therapy will be planned to reach a total minimum dose to tumor of 75 Gy as described (25). The dose of supplemental EBRT will be decided after determination of the EBRT dose equivalent delivered by the ^{153}Sm in order to reach a total minimum dose to the gross tumor volume (GTV) of 75 Gy. GTV will be defined as gross tumor on the two planning CT scans. A margin of 1.5 cm will be added to the GTV to create a clinical target volume (CTV) which will be modified to exclude adjacent normal tissues that are not involved by tumor. An additional margin of 5 mm-1 cm will be placed around the CTV to create a planning target volume (PTV) and will be dependent on treatment site and immobilization technique.

Conformal techniques such as intensity-modulated radiotherapy (IMRT) or tomotherapy will be used to plan the supplemental EBRT. The goal will be to achieve a target supplemental EBRT dose coverage of $D_{95} > 95\%$ to the PTV. Normal tissue dose constraints based on QUANTEC will be applied and respected. Standard protocols apply for supportive care based on site irradiated, and toxicity will be closely documented.

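### The dose–progression model in Section 11.3.4 treats received dose as if it varied by design, and as specified it can report a dose-response that does not exist

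*Combined protocol and SAP*

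**What the plan says.** Objective 3.2.5 (Stratum 1) is to "model any relationship between total absorbed dose and progression". Section 11.3.4 gives the method: "We will use a generalized mixed effects model treating dose and time as fixed effects and the random effect of individual patients", with progression of each targeted lesion as the outcome. It names no lesion covariate, no planned-dose analysis, no landmark and no time origin.

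The treatment plan sets one target. Section 6.2 aims to "deliver a target of 75 Gy to each and every tumor voxel while respecting normal organ constraints", and Section 6.2.5 makes the figure a floor: "Subsequent radiation therapy will be planned to reach a total minimum dose to tumor of 75 Gy". Departures are foreseen. Section 6.2 says "The total dose to be used will be modified based on surrounding tissue tolerances" and Section 11.3.3 says "The total absorbed dose delivered to each targeted lesion will be limited by the tolerance of surrounding normal tissue". Section 11.3.2 allows external beam to be adjusted for toxicity by clinical judgment. Section 11.2 keeps Stratum 1 patients in the PFS analysis even if treatment is modified or stopped.

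Section 11.3.4 also claims 80% power at alpha 0.05 on a condition that begins "If at least 10 patients have at least one lesion that receives a radiation dose with similar effectiveness to our historical control experience"; the same patients must also have a lesion at the targeted dose.

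**The concern.** A dose-response analysis is easiest to interpret when dose is assigned. Here every lesion has the same aim, and a lesion ends below it for reasons that may themselves predict progression: a difficult site, a large volume, toxicity, or treatment left incomplete. Lesions may also differ in treatment history, since Section 5.2.2 excludes only this group: "Patients who have received prior radiotherapy to all areas of current active disease are ineligible". A patient may therefore have some irradiated and some unirradiated lesions.

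The random patient effect absorbs part of the differences between patients. It does nothing about differences between lesions within a patient, which is the comparison the power statement relies on. What is at stake is that the report on objective 3.2.5 could state that higher dose delays progression when the data show only that difficult lesions do worse.

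**Working it through.** **1. The plan's own figure.** Assume 10 patients, each with one low-dose and one target-dose lesion, independent within patient. Take control as 15.8% at low dose (the historical reference in Section 11.3.1) and 80% at high dose (Section 11.3.4). The discordant-pair probabilities are 0.80 × (1 − 0.158) = 0.6736 and 0.158 × (1 − 0.80) = 0.0316, in total 0.7052. An exact McNemar test with 10 pairs then has:
- power 79.5% one-sided at 0.05, which matches the stated 80%;
- power 65.5% two-sided.

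The match rests on two readings the plan does not state: 15.8% as the low-dose rate, and a one-sided test. With 50% control in the under-dosed lesions (the lower end of the plan's expectation at 60 to 70 Gy), one-sided exact power is 18.6%. The calculation also attributes the whole difference between paired lesions to dose.

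**2. When total dose is known.** External beam starts between Days 15 and 22 (Section 6.2), so total dose is complete only weeks after registration. With exponential PFS, hazard = −ln(PFS)/6, which is 0.3075 per month at 15.8% and 0.175 at 35%. The probability of a first event by day d is 1 − exp(−hazard × d/30.44).

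| Day | PFS 15.8% | PFS 35% |
|---|---|---|
| 22 | 20% | 12% |
| 50 | 40% | 25% |
| 73 | 52% | 34% |

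Days 50 and 73 are an assumed range for the end of radiotherapy. These are underlying event times for a patient's first event, not documented progressions of a given lesion.

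**3. Lesion- and patient-level confounding, no dose effect.** Assumptions not in the documents: 20 patients, 4 lesions each, 40% of lesions hard to treat, shortfall doses 40–70 Gy, otherwise 75–90 Gy. The model is a random-intercept logistic regression of progression on dose, with a likelihood-ratio test and 400 trials per scenario. The table gives the rate of significant findings that higher dose protects (nominal 2.5%).

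| Scenario | Dose + patient effect | Adjusted for the prognostic factors |
|---|---|---|
| No confounding | 2.0% | 2.0% |
| Hard lesions short 60% vs 10%, odds ratio 2 | 11.3% | 3.5% |
| Same, odds ratio 3 | 19.5% | 4.3% |
| Same, odds ratio 5 | 30.0% | 4.0% |
| Weaker link, 40% vs 20%, odds ratio 3 | 5.5% | 1.8% |
| Early stop in poor-prognosis patients only, odds ratio 5 | 17.2% | 5.0% |
| Lesion (odds ratio 3) and stopping (odds ratio 5) together | 31.2% | 2.0% |

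Monte Carlo standard error is √(p(1−p)/400): 1.1 points at 5.5% and 2.3 points at 30%.

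**4. Early stopping triggered by progression, no dose effect.** With PFS 15.8%, 3 lesions per patient and a random-intercept model, about 7%, 14% and 33% of trials give a false positive if 25%, 50% and 75% of those who progress on treatment stop. A separate run with 3 or 5 lesions gave 9% or 8%, 13% or 15%, and 30% or 26%. The stopping fractions are assumptions.

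**5. What planned dose does and does not repair.** In a simulation with early stopping as the only mechanism, planned dose brought the rate back to about 2–3%. It cannot do the same for site. The combined plan already respects organ constraints (Sections 6.2 and 6.2.2), so planned dose carries the same site differences as delivered dose.

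**The case against.** The strongest reply is that this is a secondary analysis in a 20-patient single-arm study, that objective 3.2.5 speaks only of modelling any relationship, and that the power statement is expressly conditional. That is all true, and it limits the weight of the point. It does not answer it, because Section 11.3.4 still describes a test able to demonstrate a significant dose-response, with no adjustment or caution.

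A reader might also infer that low dose mostly marks patients who progressed and stopped. The documents do not support that:
- They give no split of causes, and the one they state most directly is normal-tissue tolerance.
- Section 9.2 lists patient or parent choice and excessive toxicity as reasons for removal, not progression.
- Section 11.1 would replace patients who do not complete treatment. Section 11.2 conflicts with this, but its inclusion rule concerns PFS.
- No response scan is scheduled during radiotherapy; restaging is about one month afterwards. Stopping for progression would need unscheduled detection.

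False-positive rates as high as 42% or 80% arise only if one lesion per patient is simulated with a rank correlation. That removes the within-patient structure of the planned model and gives a single lesion the hazard for progression of any lesion or death. With several lesions and a random intercept the rates are those in the working.

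**Conclusion.** The concern holds in this form: the exposure is received dose, it is not varied by design, the plan's own reasons for a shortfall may be related to prognosis, and the model contains nothing to separate them from dose. A spurious dose-response is possible under the analysis as written.

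The size, roughly 5% to 33% against 2.5%, is illustrative. It depends on assumed lesion counts, links between shortfall and prognosis, and stopping fractions. If hard-to-treat lesions do not have a worse prognosis, the lesion-level bias shrinks or could change direction. Because 75 Gy is a minimum, dose can also vary above target with samarium uptake, which may itself follow lesion biology.

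Two further inferences should not be drawn. No section says the result will be used to justify the dose target. And the PFS clock from registration (Section 11.3.5) cannot be assumed for the lesion model, whose time origin is simply not stated. The primary 6-month PFS analysis is untouched.

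**What to change.** In Section 11.3.4:

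1. Add baseline lesion size and site as fixed effects, and prior irradiation of the lesion where recorded. Keep the set small and prespecified.
2. Analyse the lesion dose in the combined plan, as finalised after the treatment-infusion SPECT and before external beam, alongside delivered dose. State that planned dose removes bias from early stopping but not from site.
3. As a sensitivity analysis, analyse delivered dose from a landmark at the scheduled restaging one month after external beam, in lesions progression-free at that point. Censor a lesion at resection or ablation if it has not already progressed.
4. State that the dose contrast is not designed, that the 80% power holds only if the 10-patient condition is met and the contrast is unconfounded, and that the result is an exploratory association.
5. Reconcile the 75 Gy target in Sections 6.2 and 6.2.5 with the 80 Gy in Section 11.3.3 and the 80 to 100 Gy in Section 11.3.4, so that the targeted dose in the power statement is defined.

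The cost is SAP wording and some programming, mostly on imaging and dosimetry already collected. Section 6.1 does not list prior irradiation by lesion, so it may need abstracting. Added covariates widen intervals slightly. The landmark analysis will have fewer events. If it falls 30 days after the assumed end of radiotherapy (Day 80 to 103), the formula above puts a first event before it in 55–65% of patients at PFS 15.8%, since 1 − exp(−0.3075 × 80/30.44) = 0.55 and 1 − exp(−0.3075 × 103/30.44) = 0.65. At PFS 35% the share is 37–45%. The loss per lesion would be smaller where patients have several. This is why the landmark is proposed only as a sensitivity analysis.
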